C. Long Term Objectives: 1) To decrease the long term risks associated with obesity such as coronary artery disease and diabetes in the SMI population. 2) To promote recovery, improve mental health, quality of life, and treatment adherence, and to decrease utilization of hospital resources by improving the overall medical and psychiatric condition of these patients. 3) To create a user-friendly intervention program that is easy to disseminate and implement and can be provided by any motivated health care provider in any mental health setting. 4) Finally, we wish to network with other mental health providers and create an educational website that will allow us to disseminate the program further outside of our 4 sites. Specifically, we think this will be helpful to ultimately disseminate this manualized long term weight loss program to other mental health programs such as PRRCs that are being established by the Uniformed Services Package throughout the country (3).

D. Hypotheses

1. Primary Hypotheses:

a) Veterans with SMI at four different sites with antipsychotic associated obesity who participate in the 12-month multi-modal, MOVE-like, intervention that includes classes of the Lifestyle Balance Program, and individualized lifestyle balance coaching, will gain more knowledge (i.e., greater change scores on before/after survey test instrument) about general health issues (e.g., nutrition, importance of exercise, etc.) than a control group receiving "usual psychiatric care."

b) Subjects randomized to active treatment in the 12-month, Lifestyle Balance Program will make more objective lifestyle changes (as measured by exit interviews, food and exercise diaries, fidelity assessments) than those in the usual psychiatric care group.

c) Subjects who participate in the 12-month multi-modal Lifestyle Balance Program will achieve better cardiovascular (e.g., sustained weight loss, better glucose tolerance, improved lipid profiles) and mental health (e.g., improvements in recovery from mental illness, improvement in biopsychosocial/spiritual wellness [measured by the WHO-QOL BREF and the BPSS], general measures of psychopathology, subjective quality of life, etc) outcomes than the control group.

2. Secondary Hypotheses:

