Prior to statistical analyses, the data will be inspected to determine the advisability of scale transformation to normalize distributions or reduce variance heterogeneity (e.g., logarithmic or power transformations) and to identify missing data, outliers, or other unusual features that might bias results. Where multiple measures may overlap or be redundant, preliminary analyses will explore whether it is possible to reduce these using techniques from scale development such as factor analyses. Preliminary analyses are also performed to compare treatment groups on descriptive and clinical characteristics at baseline to ensure randomization has succeeded. If there are significant differences between the treatment groups at baseline we will create propensity scores and include them in all further analyses as covariates to compensate for potential bias. We will also test if there are significant site effects, and if necessary we will include a site variable in the mixed linear model analysis, and model time as nested in subjects and subjects nested in sites.

To address concerns about excessive Type I error rates, the principal analyses are designed to answer clearly stated major research hypotheses, and are based on well-specified dependent variables. The samples are large enough to expect that confidence limits may be reasonably narrow, and findings may be robust enough to permit conservative adjustments of p-values for multiple testing. Bonferroni and other adjustments are necessarily somewhat arbitrary as Saville notes in his argument against their use (71). Additional analyses that are exploratory will be clearly identified as such. All tests will be two-tailed at $\alpha=0.05$.

2. Attrition: Dropout from treatment does not necessarily mean participants will refuse follow-up assessments, and we will attempt to obtain full follow-up data on all enrolled participants regardless of degree of participation and include all enrolled participants in analyses when any outcome data are available (intent to treat). Attrition can compromise randomization, so preliminary analyses will compare baseline characteristics

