a) SMI patients with antipsychotic associated obesity who participate in a behavioral intervention that includes classes on Lifestyle Balance will gain more knowledge (i.e., greater change scores on before/after survey test instrument) about general health issues (e.g., nutrition, importance of exercise.) than a control group receiving “usual psychiatric care”.

b) SMI patients with antipsychotic associated obesity who participate in a behavioral intervention program will achieve better cardiovascular (e.g., sustained weight loss, better glucose tolerance, improved lipid profiles, and improvement in other biological measures, e.g. insulin and c-reactive protein) and mental health (e.g., improvements in general measures of psychopathology, subjective quality of life, etc) outcomes than the control group. A larger proportion of patients who take the Lifestyle Balance classes will actually make lifestyle

changes (objectively measured by food and exercise diaries) than patients in the usual care group given ordinary counseling.

c) A larger proportion of patients who take the Lifestyle Balance classes will actually make lifestyle changes (objectively measured by food and exercise diaries and exit interviews) than patients in the usual care group given ordinary counseling. Analysis plan: For all hypotheses concerning the effects of the treatment program use analysis of repeated measures using the assessments at baseline, 8 weeks, 6 months, and 12 months. These analyses will provide information about maintenance of treatment effects. We will use a mixed general linear model with timepoints nested within patients. For hypothesis (c) we will adapt the mixed general linear model to dichotomous data by using a logistic link function to model the likelihood of life style changes. We will include all patients with at least one post-baseline data point in the analysis to maximize power. We will also consider the appropriateness of linear growth curve mixed effects models, i.e., fitting an intercept and linear slope for each treatment group as fixed effects, and separate intercepts and linear slopes for each patient as random effects. Analyses of linear trends over time with a single df effect are often more powerful tests of differences in trends than multiple df profile contrasts across the separate time points.

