It provides valid statistics even in cases where there are more potential predictors than observations, and allows us to include all demographic, psychosocial, psychiatric and medical data known at baseline as potential predictors. The results of this analysis will suggest which patients are most likely to profit from further interventions, and it will also characterize the most at risk patients.

c) Subjects will continue to give meaningful, informed consent to participate throughout the study. They will see no significant decrease in their score on the informed consent quiz given every 6 months.

Analysis plan: A general linear model (GLM): ANOVA will be performed to compare the informed quizzes score results at 0, 6, and 12 months during the subjects' participation in the study.

5. Power Analysis: All calculations are based assuming a conventional medium effect size ($f=.25$, Cohen 1988); and a two-tailed alpha set at 0.05. Tuomilehto et al. estimated the SD of weight loss at roughly 5 kg across several treatment conditions (lifestyle changes vs. control) (76). A medium effect would thus translate into a group difference of about 2.5 kg or about 5.5 pounds. With an enrollment of $N=120$ and an estimated attrition rate of 45% we expect that at least 66 subjects will provide complete the study and provide 4 data points. The power analyses below are based on a sample size of $N=66$, i.e. this is a very conservative estimate due to the fact that the mixed linear model allows us to include cases with missing values in the analyses and that while they don't provide as much information as complete cases they still provide some information and will increase power. For the between-group comparisons, $N=66$ yields power=.7199 for main differences between groups if we assume that the within subject correlation is $r=.50$. Power to test for the difference in outcome trajectories of time – our main outcome variable is 0.99, and even if the effect is as small as $f=0.15$ we will have sufficient power to distinguish between the trajectories of the two treatment groups (power=0.83) insuring that we will get significant, insuring that we Preliminary data analyses shows that these assumptions are quite conservative and that effect sizes seem to be slightly larger than projected, suggesting that the final power will exceed the estimates presented here.

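### The primary hypotheses rest on open, mismatched outcome lists, all tested at 0.05, with no named primary endpoint, time point or decision rule

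*Combined protocol and SAP*

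**What the plan says.** Section V.N.1 (General Data Analysis Issues) deals with Type I error in one paragraph. It relies on the statement that "the principal analyses are designed to answer clearly stated major research hypotheses, and are based on well-specified dependent variables". It adds that "findings may be robust enough to permit conservative adjustments of p-values for multiple testing", then remarks that "Bonferroni and other adjustments are necessarily somewhat arbitrary". It promises to label exploratory analyses as exploratory. It closes with "All tests will be two-tailed at" 0.05. No adjustment procedure is named.

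The primary hypotheses are given in section I.D and again under Statistical Plans in V.N. Both versions include knowledge, described as "greater change scores on before/after survey test instrument", and lifestyle change. Cardiovascular and mental health outcomes are given as examples. The Statistical Plans wording begins "better cardiovascular (e.g., sustained weight loss, better glucose tolerance, improved lipid profiles, and improvement in other biological measures", and its mental health list ends in etc.

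Statistical Plans specifies a mixed model over baseline, 8 weeks, 6 months and 12 months. It leaves open whether the test is a profile comparison or a linear slope. The repeated measures section (V.N.3) also mentions contrasts at individual time points.

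Section V.N.5 (Power Analysis) uses a generic f = 0.25 and "a two-tailed alpha set at 0.05". It turns this into weight: "A medium effect would thus translate into a group difference of about 2.5 kg or about 5.5 pounds". It calls the difference in trajectories the main outcome variable, without saying of which measure.

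**The concern.** A list of examples is not a specification of dependent variables. A reader of the final report could not tell from the plan which outcomes were primary, how many there were, at which time they were to be judged, or what pattern of results would confirm a hypothesis. The protection that V.N.1 relies on is therefore not delivered by the hypotheses it refers to.

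At stake is the meaning of a positive result. With many outcomes each tested at 0.05 and no stated rule for combining them, a favourable finding on one of them could be reported as support for a primary hypothesis, and its error rate could not be stated.

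**Working it through.** **1. The plan's own power figures.** Inputs from V.N.5: 120 enrolled, 45% attrition, m = 4 measurements, r = 0.50, two-sided alpha 0.05. Completers: 120 × (1 − 0.45) = 66. I used the standard repeated-measures noncentral F.

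- Between groups, f = 0.25: λ = f²Nm / [1 + (m − 1)r] = 0.0625 × 66 × 4 / 2.5 = 6.6, df 1 and 64. Power 0.716 (stated 0.7199).
- Group by time, f = 0.25: λ = f²Nm / (1 − r) = 16.5 / 0.5 = 33, df 3 and 192. Power 0.999 (stated 0.99).
- Group by time, f = 0.15: λ = 0.0225 × 264 / 0.5 = 11.88, df 3 and 192. Power 0.828 (stated 0.83).

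The figures agree for one outcome at an unadjusted 0.05, so they contain no allowance for multiple outcomes.

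**2. The two outcome lists side by side.**

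| Outcome | I.D | Statistical Plans |
|---|---|---|
| Knowledge | yes | yes |
| Lifestyle change | yes | yes |
| Weight | yes | yes |
| Glucose tolerance | yes | yes |
| Lipids | yes | yes |
| Insulin | no | yes |
| C-reactive protein | no | yes |
| General psychopathology | yes | yes |
| Subjective quality of life | yes | yes |
| Recovery | yes | no |
| WHO-QOL BREF | yes | no* |
| BPSS | yes | no* |
| **Count** | **10** | **9** |

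*Named after the hypotheses, but only for a concurrent-validity correlation.

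Merged, there are 12. Lifestyle change is counted once, although several sources are named for it. The lettering differs too: lifestyle change is (b) in I.D and (c) in Statistical Plans, where it is also repeated at the end of (b). The later reference to Primary Hypothesis C in connection with the BPSS fits only the I.D lettering. The WHO-QOL BREF is in neither the schedule of events nor the assessment descriptions in V.G, and recovery has no named instrument.

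**3. Chance of at least one false positive, all nulls true, each test at 0.05.** For independent tests this is 1 − 0.95^k. For equally correlated tests I integrated numerically over a shared normal factor. The correlations are assumptions; the documents give none.

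| k | Independent | ρ = 0.3 | ρ = 0.5 | ρ = 0.7 |
|---|---|---|---|---|
| 3 (one per hypothesis) | 0.143 | 0.136 | 0.125 | 0.109 |
| 9 (Statistical Plans) | 0.370 | 0.326 | 0.269 | 0.202 |
| 12 (merged) | 0.460 | 0.397 | 0.319 | 0.232 |

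Time-point contrasts and the choice between profile and slope tests are not counted.

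**4. Cost of adjusting over all 12 instead.** At alpha 0.05/12 = 0.00417, the powers in step 1 become 0.353, 0.987 and 0.516.

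**5. Power of a simple 12-month weight comparison.** Inputs: 2.5 kg, SD 5 kg (d = 0.5), 33 per arm (1:1 assumed; the ratio is not stated). Noncentrality is 0.5 × √(33/2) = 2.03 on 64 df, giving power of about 0.52. With all 120 retained, it is 0.5 × √(60/2) = 2.74, giving about 0.78. Neither is the stated 0.72 or 0.99.

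**The case against.** The strongest reply has four parts.

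- **No decision rule is written.** The plan never says that one significant result suffices, and the combined hypothesis asks for better cardiovascular *and* mental health outcomes. This stands: the percentages in step 3 depend on an any-one-outcome rule that is assumed. It does not rescue the plan, because the rule is still missing.
- **The plan does not claim formal control.** It says it is addressing concerns, allows that adjustment may be possible, and will label exploratory work. This also stands, but nothing is committed, and labelling exploratory analyses does not help when the multiplicity lies within the primary hypotheses.
- **Factor analysis would reduce the number of tests.** V.N.1 limits it to overlapping measures as a preliminary step. Done on pooled data, it need not inflate error. It is a weakness only in that the final set of variables is left open.
- **The power section names a main outcome.** It names a kind of test, the difference in trajectories, which applies to any scale. Weight enters only as a translation of a generic effect size.

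A reader might also infer that the BPRS, CGI and Hamilton scale are listed as primary outcomes. They are not. The primary hypotheses speak only of general measures of psychopathology; the BPRS is named in the secondary hypotheses, and the other two appear among the assessments. The count of 12 does not use them.

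**Conclusion.** The concern holds in this form: the stated safeguard, well-specified dependent variables, is contradicted by open outcome lists that differ between two sections. No primary endpoint, time point, ranking, adjustment or decision rule is committed.

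Under an any-one-outcome rule, the false-positive chance is 37% for 9 and 46% for 12 independent outcomes, and between 20% and 40% for correlations of 0.7 to 0.3. With one independent test per hypothesis it is 14%. All are well above 5%. These rest on three assumptions: the rule, the tally of outcomes and the correlations.

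A reader might go further and say that the trial has a 46% error rate, or that the plan falsely claims error control. The documents support neither. The first depends on a rule the plan does not state and on independence; the second overstates a paragraph that only sets out to address the issue.

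**What to change.** - **Primary outcome.** Name weight, the only outcome V.N.5 translates into a detectable difference. Test it once at two-sided 0.05 with the planned mixed-model group-by-time test over baseline, 8 weeks, 6 months and 12 months, the kind of test V.N.5 powers. State that this is the 3-df profile test, or choose the slope and restate the power.
- **If a 12-month contrast is preferred,** restate its power. A simple comparison of 66 completers has about 0.52; a mixed model may recover some of the loss, but this has not been calculated.
- **Crossover.** Sections V.E and V.L let usual-care patients take up the active program after 6 months. State how their later data are analysed. This is essential for a 12-month contrast, and the trajectory test also uses the 12-month value.
- **Secondary outcomes.** Replace the two lists with one closed list under one lettering, each item with an instrument and time point. Test it in a fixed order or with Holm, or report intervals only.
- **Composites.** Fix any factor-analytic composite on pooled data, blind to arm.

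The cost is SAP and hypothesis wording, plus a power recalculation if the contrast changes. No new data are needed. The downside is that the other outcomes can no longer carry a primary claim; in exchange, the primary test keeps its full 0.05.

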In summary, our ongoing research has been quite successful at achieving weight loss. It is to our knowledge, the longest term intervention proven effective in SMI patients (often dually diagnosed with substance abuse) with antipsychotic medication associated obesity. This program may close a gap in care for those patients who cannot or do not access MOVE!. Continuation of this work is crucial to see if we can optimize the maintenance effects of this program as well as disseminate this work.

V. Research Design and Methodology

A. The study is a multi-site, randomized, open, effectiveness trial with masked raters blind to treatment condition. 120 veterans (30 at each of 4 sites) will be randomized for participation in this study. The 4 sites and primary Co-investigators are:

West Los Angeles VAMC	Brentwood, CA	[name]
Long Beach VAMC	Long Beach, CA	[name]
Sepulveda, VAMC	North Hills, CA	[name]
Los Angeles Ambulatory Care	Los Angeles, CA	[name]

B. The oversight and organization of the multicenter trial across all 4 sites will be coordinated by [name] as the Principal Investigator and her Program Manager located at the West Los Angeles site. At each of the 4 sites there is a designated co-investigator who will be responsible for weekly team meetings of all research staff that will encompass clinical and research issues. The overall PI will arrange a study start up meeting and monthly coordinating meetings to facilitate fidelity of the project between all 4 sites. Weekly coordinating meetings will be necessary during the first 6 months of start up.

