The first 6 months will be used to hire and train all staff from all 4 sites on the intervention. The dietician from the West Los Angeles site has updated the class materials. We will be responsible for training all the health coaches at each of the 4 sites. The first 6 months of the grant funding period will also be used in part, to establish inter-rater reliability of raters for all study measures. Our study consultant, [name], will assist with helping assure there is fidelity of all lifestyle balance coaches in their presentation of class materials and in their handling of veteran's progress in the research study. [name] is an international expert in psychosocial skills training for patients with schizophrenia. The educational modules he developed to help with illness management have been disseminated all over the world. Thus, his expertise at dissemination of psychoeducational materials and a fidelity rating instrument to check on adherence to the intervention by the lifestyle balance coaches has been developed.

During the first 6 months of start-up time for the 3 new sites, we will need to develop a list of exercise options for each site from which veterans can choose to participate. At West LA VAMC a number of exercise options already exist and it is hoped that equivalent options can be developed at each site. Of note the most frequent option for exercise that was chosen was walking, so recommendations for walking trails, and/or development of a schedule for walking groups would be something that will need to be developed at each of the three new sites. Peer-to-peer exercise options (encouragement of groups of veterans to exercise together) can be developed at all 4 sites. Wellness programs and supervised exercise options through the department of physical medicine for those patients with cardiac problems are available at all 4 sites.

A web based data entry system and web page for our coordination of our program will be developed and completed. Case report forms will be available on the web page as well as a study bulletin board. The data management team from the VISN 22 MIRECC will finalize the web page and web based data entry system and assure that it is working at all 4 sites.

C. Inter-rater Reliability:

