programs (that are converting to PPRCs) from which to recruit. There are 10,000 patients classified as SMI within these three medical centers. Long Beach hospital also has a large outpatient as well as an inpatient program from which to recruit. Long Beach hospital served over 10,000 mental health unique veterans in 2008, of which probably half of these are SMI. To assist doctors in identifying which patients under their care are eligible for our study, we intend to obtain Waiver of HIPAA for screening purposes. With this we can obtain from the VA a list of eligible patients and approach their doctors to notify them of their eligibility and what the program involves so that the doctors can effectively discuss it with those patients and direct them to us. Finally, we intend to utilize social media to spread word of the study, requesting mention of it be made by the GLA VA Facebook page.

One hundred twenty patients clinically determined to require ongoing treatment with SGAs who have experienced 7% or more increase in weight or whose BMI has become greater than or equal to 25 during treatment with an SGA will be randomized to receive either the Lifestyle Balance Program (a MOVE! like behavioral weight loss intervention with psychoeducational classes) or Usual Care. These inclusion criteria have been chosen to selectively recruit only subjects whose adiposity is both clinically pertinent and reasonably construed to be due to the introduction of an antipsychotic. All patients will be asked to sign informed consent. Patients who are unable to give informed consent will not be entered into the study. Subjects with a history of substance abuse or dependence cannot participate in this study unless they are sober for three months. If a patient has a legal conservator, and wants to participate in the study, he or she will need the legal conservator to sign informed consent. If a patient is too medically ill to be involved in any type of exercise or weight loss program he or she will be excluded from the protocol (e.g. a patient with cancer on chemotherapy who is vomiting and losing weight should not be entered into this study).

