3. Repeated measures analyses: We propose to longitudinal (repeated measures) analyses to maximize the additional power we gain by observing the same subjects across 12 months.. Repeated measures analyses permit contrasts at each time point, and also describe and compare trajectories of change (trends), speed and durability of effects. We will also conduct separate cross-sectional to provide outcome data for ongoing safety review, interim progress reports, study oversight and conduct.

The primary design for longitudinal (repeated measures) analyses of continuous outcome scales will be a 2-group (treatment) mixed general linear model of timepoints nested within participants. This is very general linear model that permits flexibility in specifying the nature of the covariances among the dependent measures, allows time-dependent, within and between subject covariates, and permits incomplete (i.e., missing) data. Analyses of trends across the monthly assessments will be done using growth curve model within the mixed model analysis of covariance design with repeated measures described above. We propose to model a linear trend of time unless inspection clearly suggests nonlinearity. By fitting a slope over time (and intercept) for each participant who has baseline and at least one other measure, this method makes good use of all the data, and is robust even if some of the some measures are missing. The use of the mixed general linear model for all cross-sectional and linear hypotheses ensures that results will be comparable across different analyses and provide a framework to include group, person and time-specific covariates if it becomes necessary. The preliminary analyses have shown that this analysis strategy provides meaningful results even with partial data and suggests that we will exceed the originally projected power.**4. Stratification:** Randomization will be stratified by type of antipsychotic and presence of mood stabilizer medication (e.g., depakote, lithium) to assure balance on olanzapine and clozapine by randomizing within three strata – olanzapine, clozapine, and all other antipsychotics -- using three separate randomization lists. Because such stratification can adversely affect statistical power by creating artificially comparable (and heterogeneous) groups, two dummy variables coding olanzapine and clozapine at baseline will be included in all analyses as covariates.

4. Statistical Plans:

Primary Hypotheses:

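### Allocation is not balanced on site and site enters the model only after a pretest; balancing on site and fixing a site term is a cheap improvement with a small gain in precision

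*Combined protocol and SAP*

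**What the plan says.** Section V.A sets the size and spread of the trial: "120 veterans (30 at each of 4 sites) will be randomized for participation in this study". The stratification paragraph, which follows the repeated-measures text in V.N, opens with "Randomization will be stratified by type of antipsychotic and presence of mood stabilizer medication". It then implements this by randomizing within three antipsychotic groups, "using three separate randomization lists". For the analysis it fixes only the drug strata: "two dummy variables coding olanzapine and clozapine at baseline will be included in all analyses as covariates".

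Site appears in V.N.1, General Data Analysis Issues. Site effects are tested for significance first, and "if necessary we will include a site variable in the mixed linear model analysis", with subjects nested in sites.

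Several features differ by site. The start-up text in Section V says of coaches: "We will be responsible for training all the health coaches at each of the 4 sites". Of exercise it says: "we will need to develop a list of exercise options for each site from which veterans can choose to participate". Equivalence with West Los Angeles is only hoped for. The inclusion section lists different patient sources for the different centers.

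The documents give no block size, allocation ratio, site-level list or other device that would balance the arms within a site.

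**The concern.** The program reaches patients through a site's coaches, classes and exercise facilities, and one of the four sites already ran the preceding trial. Site is therefore a plausible predictor of weight change. With three drug lists and no site factor, the split between arms at a site of 30 is left to chance. A lopsided site can cost precision and load coaches unevenly. If site is then omitted from the model, differences between sites add noise to the arm comparison. The plan also leaves the primary model open, because whether site is in it depends on a test run on the trial data.

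**Working it through.** **Inputs from the documents.** N = 120, 30 per site, four sites (V.A). SD of weight loss 5 kg, planned difference 2.5 kg (f = 0.25), attrition 45%, four data points, within-subject correlation 0.50, two-sided alpha 0.05 (V.N.5).

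**Assumptions.** 1:1 allocation, since the text says only that patients "will be randomized to receive either the Lifestyle Balance Program" or usual care. Block sizes of 4, 6, 8 and 20; three drug mixes; sites drawing from common lists in random order. Site means of weight change with SD 1, 2 or 3 kg.

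**The plan's own power first.** Completers: 120 × (1 − 0.45) = 66. For the between-group effect, λ = f²·N·m / (1 + (m − 1)ρ) = 0.0625 × 66 × 4 / 2.5 = 6.6. With 1 and 64 df the power is 0.716, against 0.7199 stated. The figure reproduces.

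**Chance imbalance within a site.**
- Unrestricted allocation, one site: 2 × P(X ≥ 20), X ~ Binomial(30, 0.5), = 0.0987. At least one of four: 1 − (1 − 0.0987)⁴ = 0.340.
- Overall split held at 60:60, one site (hypergeometric): 0.057.
- Three blocked central lists, simulated (15,000 runs per setting): at least one site at 20:10 or worse in 19% to 20% of trials. Block size and drug mix barely change this.
- Lists split by site and drug stratum, blocks of 4 or 6: 18:12 or worse at any site in about 0.3% to 2% of trials; 20:10 did not occur in 15,000 runs. Without site, 18:12 or worse occurs in about 68% to 83%.

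**Cost when site is in the model.** In a single-endpoint model, SE = 5 / √(Σ n₁n₀/(n₁ + n₀)), summed over sites. With perfect balance the sum is 4 × 7.5 = 30 and SE = 0.913 kg. Mean efficiency relative to that is about 0.975 with blocked central lists and 0.967 with unrestricted allocation:
- 0.913 / √0.975 = 0.925 kg, a loss of 1.3%
- 0.913 / √0.967 = 0.928 kg, a loss of 1.7%

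The 5th percentile of efficiency is about 0.92 to 0.94, a loss of 3% to 4% in an unlucky trial. For power, λ = 6.6 × 0.97 = 6.40 with 1 and 61 df gives 0.702, against 0.715 at full efficiency. Even 20:10 at every site (efficiency 4 × (20 × 10/30)/30 = 0.889) gives 0.66.

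**Cost under each analysis rule** (simulated, 120 patients, residual SD 5 kg):

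| Rule | Site SD 1 kg | 2 kg | 3 kg |
|---|---|---|---|
| Site never modelled, not balanced | about 0.92 | about 0.97 | about 1.04 |
| Plan's test-then-adjust, not balanced | 0.91–0.93 | 0.91–0.93 | 0.91–0.93 |
| Site balanced | about 0.91–0.92 | about 0.91–0.92 | about 0.91–0.92 |

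Type I error was about 4.7% to 5.7% under test-then-adjust and 4.5% to 5.5% with site ignored.

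**How often the site test detects a difference.** With 30 per site: about 31% at site SD 1 kg, 71% at 2 kg and 88% at 3 kg. With about 16 completers per site (66/4 = 16.5): 18% at 1 kg and 51% at 2 kg. So the pretest misses a 2 kg site SD about half the time. It costs little precision all the same, because it tends to miss when the observed site means lie close together.

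**The case against.** The strongest reply is that modelling site is an accepted alternative to stratifying on it, and V.N.1 provides for it. That largely stands: under the plan's own rule almost all of the precision is recovered. A site SD of 2 to 3 kg is also large beside a planned treatment difference of 2.5 kg, and at 1 kg the penalty nearly vanishes whatever the rule.

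Three further points stand. No treatment effect per site is planned, so a thin arm at one site does not defeat a stated analysis. The 34% figure rests on independent coin flips; lists meant to secure balance would probably be blocked, which brings it to 19% to 20%. And the text does not rule out a set of three lists at each site. It never says so, however, so clarification is needed in either case.

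A reader might infer that chance imbalance biases the treatment effect. The documents do not support that: assignment is random with respect to site, so the estimate is unbiased and the test keeps its level. A reader might also take the unmodelled figures (0.97 against 0.91, 1.04 against 0.92) as a 7% to 13% penalty of this plan. They belong to an analysis that never includes site, which is not what V.N.1 describes.

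What the reply does not remove is the conditional site term. The drug dummies are fixed in all analyses; site is not.

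**Conclusion.** The point holds as a modest, inexpensive improvement and not as a threat to validity. Marked imbalance (20:10 or worse) at one or more sites has a chance of about one in five to one in three, and 6% to 10% at any given site. The expected cost under the plan as written is about 1% to 3% in standard error; if site is adjusted for, main-effect power is about 0.70 against 0.715. Larger losses require both a site SD of 2 kg or more and a model without site.

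These figures assume 1:1 allocation, a residual SD of 5 kg and a single-endpoint simplification of the mixed model. The site SDs are assumptions, as the documents give none. If the three lists are in fact held separately at each site and blocked, the imbalance largely disappears and only the pretest remains to be changed.

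**What to change.** - State how the lists operate across the four sites, with the allocation ratio and the method of restriction.
- Balance allocation on site as well as drug stratum, for example by minimization with a random element on these two factors. Fully crossed lists would give 4 × 3 = 12 cells, sparse for clozapine at some sites.
- Reconcile the mood-stabilizer factor, which the stratification paragraph names but three drug lists cannot implement. Crossing it in as well would give 24 cells, an average of 5 patients each.
- Replace the site pretest in V.N.1 with a fixed site term in all primary models, alongside the two drug dummies.

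Cost: protocol wording, and allocation set-up in a web system that is still to be developed and for which the documents describe registration and data entry but no allocation function. The site term uses three degrees of freedom. Balancing within site makes the next assignment slightly easier to guess in an open trial; a random element, or variable block sizes if blocks are used, limits this but does not remove it.
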